Protocol & Statistical Analysis Plan

Official Title: Influence of Exercise on Neurocognitive Function in Breast Cancer

NCT02793921

Document Date: 6/14/2023

Title of study:

Exercise Program in Cancer and Cognition (EPICC)

Brief description:

This is a single-site randomized control trial to test whether a moderate-intensity aerobic exercise intervention can prevent cognitive decline in postmenopausal women with breast cancer. Women who meet the eligibility criteria will be randomly assigned to either receive the intervention or usual care. Data will be collected prior to initiating endocrine therapy for breast cancer (TP1) and approximately 7 months later (TP2) and include fitness testing and a battery of neuropsychic tests, blood biomarkers, and other behavioral measures; a subset of women will undergo MR imaging. For women who agree to additional follow-up, data will also be collected approximately 12 months post TP1 (TP3).

Specific aims:

We will examine whether a well-controlled and monitored site-based exercise intervention improves cognitive function in postmenopausal women with early stage breast cancer. 1. Compared to usual care, examine whether the 6-month exercise intervention improves cognitive function in postmenopausal women with early stage breast cancer. Hypothesis 1. Exercise will improve cognitive function in women receiving AI therapy in a domain specific fashion such that attention, executive and memory functions will be influenced more than other domains.

2. Compared to usual care, examine the direct effects of exercise on neuroimaging metrics of brain health including regional gray matter volume, white matter architecture and functional dynamics of the brain and the pro-inflammatory biomarkers (IL-6, TNF- α), and explore the direct effects of exercise on symptoms (fatigue, sleep problems, depression, anxiety). Hypothesis 2. Exercise will improve neuroimaging metrics of brain health and pro-inflammatory biomarkers.

3. Compared to usual care, explore whether the effects of exercise on cognitive function are mediated by a) neuroimaging metrics of cognitive function, b) IL-6 and TNF- α levels, c) symptoms (fatigue, sleep problems, depression, anxiety), d) and moderated by E2 levels over the first six months of AI therapy.

Inclusion criteria:

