1. Postmenopausal women, defined by lack of a menstrual period for an entire year or confirmed by physician 2. 18-80 years of age 3. Able to speak and read English 4. Completed a minimum of 8 years of education 5. Diagnosed with stage 0, I, II, or IIIa breast cancer, confirmed by medical record 6. Within 2 years post-completion of primary treatment 7. Will be at least two weeks post-breast conserving surgery or three weeks post-breast conserving surgery with sentinel lymph node biopsy or four weeks post-mastectomy at the start of participation.

Exclusion criteria:

1. Prior treatment with cancer chemotherapy, central nervous system radiation, or intrathecal therapy 2. Prior cancer involving the central nervous system 3. Clinical evidence of metastatic disease 4. Any of the following breast cancer surgery complications unless approved by the participant's health care provider: persistent seroma requiring aspiration, wound dehiscence, infection, prolonged drain output, lymphedema 5. Reconstructive surgery unless approved by the participant's health care provider 6. Any significant medical condition that would preclude them from exercising (e.g., uncontrolled diabetes, congestive heart failure, angina, uncontrolled arrhythmia or other symptoms that indicate increased risk for an acute cardiovascular or

Research activities:

Participants: We plan to recruit up to 350 postmenopausal women with early-stage breast cancer: up to 127 will undergo an exercise intervention in this 6-month study described below and up to 127 will be enrolled in an usual care arm. A subsample of women who are randomized will participate in the neuroimaging component of the study (n=150; 75/group).

Locations: Recruitment will take place at St. Clair Budway Surgical Associates and Magee-Women's Hospital of UPMC, Comprehensive Breast Care Center at UPMC Passavant-Cranberry, UPMC South Hills, UPMC McKeesport and Magee Woman care Center in Monroeville. Data collection will take place in participants' homes, at the University of Pittsburgh School of Nursing and Sennott Square or Healthy Lifestyle Institute offices in Oak Hill. The exercise intervention will take place at Sennott Square, Baierl Family YMCA, Sampson Family YMCA, and JCC South Hills Branch or Healthy Lifestyle Institute offices in Oak Hill; alternatively, a participant may exercise in her home or other location of her choosing. MRI Imaging will take place at Carnegie Mellon University SIBR.

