Informed Consent: Written informed consent will be obtained from the participant prior to any study-specific activities either in person or remotely.

Assessments: Participants will complete a series of assessments at two timepoints; Time 1(baseline) will occur up to 2 years post-completion of primary treatment and before randomization and initiation of the exercise intervention/usual care. Time 2 will occur approximately within 1 month of completion of the intervention (or 7 months post-Time 1). Data collection at each timepoint will be composed of behavioral assessments, blood samples, neuroimaging and objective measures of physical activity and fitness. We will also objectively evaluate physical activity at 3 time points during participation (approximately every 5 weeks). For participants who agree to additional follow-up via the addendum consent form, Time 3 will take place approximately 6 months post Time 2 and will consist of blood work, fitness testing and behavioral testing as described below. We will also objectively evaluate physical activity at midway (3 months) between Time 2 and Time 3 as well as at Time 3. Participants will also be asked to maintain their edema cap and REDCap diaries during this time. Participants may be asked to complete assessments in two separate sessions at both TP1 and TP2. During one visit (which includes fitness testing), blood samples (approximately 30cc or 6 teaspoons) will be collected for biobanking for future evaluation of the relationships of biomarkers (including genetic biomarkers) with cognitive function, exercise, brain health and symptoms. Blood samples will be transported immediately, under conditions appropriate for preservation of the blood, and stored before the end of the day of testing. Samples will be maintained in a -80°C freezer in the Victoria building under the control of the principal investigators of this research project and will be maintained indefinitely. In the event that we need to send samples to a different facility outside of the University of Pittsburgh for analysis in the future, no identifying information will accompany the sample. Participants will be asked questions prior to the blood draw to determine any factors which may affect the findings. If a recent illness is noted, or certain other factors as noted on the form, are found, the participant may not be eligible for a blood draw at this visit. In this event, we will attempt to collect the blood at another time, either during a subsequent visit or other agreed upon time. Fitness will be objectively measured at Time 1 and Time 2. This test takes 15-30 minutes to complete. Subjects will be given exercise testing instructions regarding proper clothing and footwear and will be told to abstain from caffeine or nicotine 2 hours prior to the physical activity/fitness assessment. When participants report to the laboratory (Sennott Square) for the fitness assessment they will first be acquainted with the equipment, allowed to ask any questions, and get comfortable with walking on a treadmill. Before the test begins, the participant will get familiar with wearing the mouthpiece and nose clips or facemask required during the test in order to measure cardiovascular fitness. This helps to reduce anxiety associated with exercise and fitness testing. Cardiovascular fitness testing consists of progressively increasing exercise intensity while the subjects exhaled air is collected via a mouthpiece that is connected to a gas exchange chamber via a breathing tube. A comfort fitted head gear supports the mouthpiece. This reduces the effort of the participant to keep the mouthpiece in the correct position throughout the test. Alternatively, the participant may wear a facemask. The gas chamber that is being used is the Parvo Medics True one 2400 metabolic cart, which is one of the most widely accepted systems in scientific research. Next we will provide the participant with adequate warm-up and stretching which will be monitored by the exercise physiologist. After 5-10 minutes of warm-up, the participant will walk on a motor-driven treadmill at a constant speed with increasing increments of the incline. We will conduct a submaximal vo_2 fitness test which estimates the maximal oxygen capacity for the individual without reaching an exhaustive level. The sub-maximal graded exercise test is a modified Balke protocol in which the speed remains constant and grade is increased 1% each minute. This protocol has been used extensively in the literature for fitness training for both normal, at-risk, and impaired populations. Verifying maximal vo_2 is difficult in at-risk

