
populations and therefore submaximal vo_2 is often the desired method. This method has people walk at a slow - moderate pace with increasing grade increments up to the goal heart rate of 85% of the age-based maximum (220-age) or a rating of perceived exertion equal to or greater than 15 for those individuals whose heart rate response is blunted due to medication. This approach does not require the attendance of a physician because it is within the safe heart rate work zones and leads do not have to be attached to the participant. The submaximal vo_2 assessment usually takes about 15 - 30 minutes to complete depending on the starting fitness level of the participant. During the exercise test, heart rate is continuously monitored along with blood pressure readings every two minutes. The blood pressure is obtained by the Sentech Tango 2 automated unit. This blood pressure unit is designed for exercise testing and has been tested as a valid and reliable system to measure blood pressure during exercise. When the subject reaches the endpoint goal of the exercise test, the mouthpiece and head gear will be removed and they will undergo a four minute active cool-down in which they will walk at a slower rate with zero incline grade. After these four minutes the participant will be helped off of the treadmill and undergo a passive cool-down session in which they are seated in a chair. The participant's heart rate and blood pressure will be continuously monitored through the cool-down period and the participant will not be allowed to leave until the vital signs return to normal patterns. Blood pressure will also be monitored both before and after the fitness test to ensure that changes in blood pressure resulting from exercise are all normal. If the participants vital signs remain elevated after a cool down and rest period, the study physician will be called and will provide instructions for further monitoring of the participant. Situations like this are very rare and occur in less than 1/10,000 instances of fitness testing. These assessments will be conducted in [name] laboratory by an exercise physiologist with >15 years of coaching and exercise testing who is AED and Recertified and has certifications in exercise physiology from the American College of Sports Medicine. Prior to engaging in exercise, participants may be fitted with one or two physical activity monitoring devices (Body Media Sense Wear mini armband or Autographing). The Body Media Sense wear Armband is worn around the upper left arm. Hectograph Link is a wristband worn on the non-dominant arm. Both devices will record physiological data (e.g., heat flux, sweat rate, etc.) over the duration of their exercise test; this information is used in an algorithm to determine intensity and amount of physical activity. The participants will be provided with detailed instructions regarding wearing of the device(s) as well as the option to remove the device(s) if it becomes problematic. Participants may also be asked to wear the physical activity monitoring device(s) for a week before or after the exercise testing session. This way we can get a more comprehensive idea of both activity and fitness levels. In addition, all participants, regardless of group assignment, will be asked to wear the device(s) 3 additional times through their participation in this study(approximately every 5 weeks) and again at the follow-up assessment (TP2) for total of 5 times over the course of participation in the study. Participants who wear the Actigraphy Link will be given a log at the time they receive their device. This log is used to report any time/reason the device is removed as well as information about their sleep. The self-report information contained in the log will be compared to and used in interpreting the device data. Alternatively, in the event that a participant cannot come to Sennott Square for this testing for any reason (e.g., preference, weather, pandemic-related restrictions.), a brief heart-rate monitoring session may take place virtually either by phone or teleconferencing. During this guided session, the participant will be asked to wear study-provided heart rate monitor for approximately 5 minutes and asked to report readings to study staff. Participants will also be asked to report their weight; home scale may be provided for participants to use (with instructions to return via pre-paid mailer when complete). Data from the session can provide information to estimate results from a VO_2 test. Participants may also be asked to complete questionnaires regarding exercise knowledge and self-efficacy during the physical activity and fitness assessment, time permitting. Alternatively, these may be included in the behavioral assessment. The behavioral assessment includes a battery of standard clinical neuropsychological tests that assess verbal ability, visuospatial ability, attention/processing speed, memory, and executive function, will be administered. These tests have standard administration protocols and will be administered by trained staff. This is expected to take approximately 90 minutes. We will also administer measures of demographics, mood and quality of life. The tasks and measures will include those listed in section 2.8. All of the tests will be identified by the subject ID and not by name. At times these tests can be mentally fatiguing or frustrating. Subjects will be told that the tests are designed to be challenging and that they should just perform to the best of their abilities. They will also be offered breaks as needed between tests to help reduce fatigue and frustration. Data collected will be transported by the research personnel immediately following the assessment if conducted in the participant's home to the office of the PI in the

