eDEM Cap: All participants will be provided with the electronic Drug Exposure Monitor (Edema) to measure adherence to hormonal therapy. The Eden consists of a bottle cap fitted with a microprocessor that records the date and time the cap is removed from a medication vial. It also records the duration of time that the cap is off the vial. Each monitor has sufficient memory to record and store the dates and times of 2000 doses. The Eden will be collected at the time of the follow-up assessment. Neuroimaging** No new MRI participants will be consented after February 2020 ** A subgroup(N=150) will have the following neuroimaging protocol at times 1 and 2. Each session will last approximately 1 hour. Seventy-five women from each group will be randomly sampled to participate in neuroimaging based on age and baseline executive function. On the day of a participant's scan, she will be asked to arrive 30 minutes before the start of her scan in order to provide time to review and sign a separate CMU consent form, and to undergo final safety screening by a SIBR MRI technologist. For the sake of brevity, MRI sequence parameters have been omitted but can be found in our prior publications.^{68,75,78,132,133} Brain Morphology: High-resolution anatomical MPRAGE (1mm³ voxels, 256 slices) images will be used for morphologic and volumetric analyses. The Free Surfer pipeline using its longitudinal option will be employed to compute cortical and subcortical volumes, cortical surface area, and thickness. Intracranial volume (ICV) will be used as a covariate in analysis of brain morphology. Regional values that can be exported into statistical packages (e.g., SAS) will be calculated. Errors and omissions will be corrected according to standard guidelines. Hippocampal subfields: We will use a focal (.4 x .5x 2mm) T2-weighted sequence for hippocampal subfield segmentation¹⁴⁶. Since the dentate gyrus and CA1 subfields are more frequently affected by exercise^{147,148} and the head of the hippocampus may be affected more than the tail,⁶⁸ this will allow us to segment hippocampal subfields to determine regional specificity of the intervention. White matter imaging will be performed using diffusion-weighted sequence (50 directions; 2.5mm isotropic voxels). Images will be corrected for head motion and eddy current artifacts. For each voxel the first three principle eigenvectors of water diffusion will be calculated using FSL, which will be used to calculate fractional anisotropy (FA), axial and radial diffusivity components. These maps will be transformed into standard space using non-linear normalization. We will also conduct fiber tractography, which identifies tracts between regions and will use computational methods to dissociate crossing white matter fibers within voxels.¹⁴⁹ Finally, white matter lesions (see next section) will be removed from the calculation of white matter integrity. White matter hyperintensities (WMH): We will use a T2 FLAIR sequence and an automated segmentation method, which uses an algorithm for automated selection of WMH lesions. The segmented WMH are then localized to white matter tracts using the Johns Hopkins White Matter Atlas. Resting state analyses: We will employ standard BOLD sequences used by PI: [name] and graph theory approaches. Prior to generating brain networks (see¹⁵⁰), all images will be motion corrected and registered. To control noise,¹⁵¹ data will be preprocessed to remove white matter, and cerebrospinal fluid signal. Motion scrubbing will be performed.¹⁵² Heart rate will be used to correct for physiological confounds. The time series from each node will be compared to every other node using regression analysis, generating a correlation matrix. A threshold is applied to the matrix to retain only the strong connections and is maintained to represent connection strength.¹⁵³ Once an adjacency matrix is generated, network attributes can be calculated for each node. The data will allow for the identification of changes in network topology that are associated with the intervention. Cerebral Blood Flow(CBF) will be measured with multi-phase pseudo Continuous Arterial Spin Labeling(pals) with background suppression and will be analyzed using BASIL. Task-evoked activation: We selected the n-back working memory paradigm because our preliminary data demonstrates that walking interventions improve performance on this task.¹⁵⁴ The task also has high reliability and involves a broad network of brain regions including the PFC, ACC, hippocampus, and basal ganglia.¹⁵⁵ Participants determine whether a lowercase letter

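### Do the entry rules fail to secure a baseline before endocrine therapy, and does that undermine Hypothesis 1 or the E2 analysis?

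*Combined protocol and SAP*

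**What the plan says.** The Brief description places baseline before endocrine treatment: "Data will be collected prior to initiating endocrine therapy for breast cancer (TP1) and approximately 7 months later (TP2". Under Specific aims, Hypothesis 1 reads "Exercise will improve cognitive function in women receiving AI therapy", and Aim 3 explores whether exercise effects are "moderated by E2 levels over the first six months of AI therapy". Aim 1 itself is stated for postmenopausal women with early stage disease and does not mention AI therapy.

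The operational text uses a different anchor. The Inclusion criteria require entry "Within 2 years post-completion of primary treatment", and the Assessments section says "Time 1(baseline) will occur up to 2 years post-completion of primary treatment and before randomization". Neither mentions endocrine therapy. The Exclusion criteria break off in the middle of item 6, so any later item cannot be read.

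Two further places bear on the point. The eDEM Cap section states "All participants will be provided with the electronic Drug Exposure Monitor (Edema) to measure adherence to hormonal therapy", and the cap logs the date and time of each opening. On baseline data, the Assessments section says "The tasks and measures will include those listed in section 2.8"; that list is not part of the text available. The Analysis Plan for Aim 3 adds E2 and its interactions to the Aim 1 models without saying which E2 measurement is used.

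**The concern.** If endocrine therapy may begin well before Time 1, three things blur: the population that Hypothesis 1 describes, the meaning of baseline, and the AI period that the E2 question refers to. If AI therapy started when primary treatment ended (an assumption), a woman entering 6 to 24 months later would contribute nothing from her first six AI months. That is 18 of the 24 permitted months.

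For Aim 3, a mix of AI phases could also let the E2 interaction pick up differences between phases rather than between E2 levels. Endocrine status at Time 1 is not a named covariate or a minimization factor, and an E2 value taken during the study is measured after randomization.

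**Working it through.** The plan gives no figure on this point to reproduce. The check sets the texts against each other and then bounds the consequences with assumed inputs.

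**Can the statements all hold?** Yes. A woman can be within 2 years of primary treatment and not yet have started endocrine therapy. The Brief description supplies the endocrine condition and the other two sections supply the outer limit. The eDEM Cap text expects hormonal therapy on study in every participant. It does not establish the drug class or the start date.

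**How much of the first six AI months is observed?** Let s be the AI start in months relative to TP1, with TP2 at 7 months. Overlap = max(0, min(7, s + 6) − max(0, s)).

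| s | −6 | −3 | 0 | 1 | 3 | 5 | 7 |
|---|---|---|---|---|---|---|---|
| Overlap (months) | 0 | 3 | 6 | 6 | 4 | 2 | 0 |

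A start at or shortly after TP1, as the Brief description implies, gives the full six months.

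**Aim 1.** Assume a 50/50 phase mix (p = 0.5) and a difference d in mean change between phases, in SD units. Left out of the model, phase multiplies the standard error by √(1 + p(1−p)d²):
- d = 0.2: √(1 + 0.25 × 0.04) = 1.005
- d = 0.5: √(1 + 0.25 × 0.25) = 1.031

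Randomization keeps the comparison unbiased in either case.

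**Aim 3.** Assume no true E2 moderation, p = 0.5, an exercise effect differing by δ SD between phases, and an E2–phase correlation r. The spurious interaction per SD of E2 is δ·r·√(p(1−p)) = 0.5·δ·r. It runs from 0.5 × 0.2 × 0.3 = 0.030 to 0.5 × 0.3 × 0.7 = 0.105.

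With the maximum of 2 × 127 = 254 women (Research activities, Participants) and residual SD 1, the interaction's standard error is about √(4/254) = 0.1255, or 0.127 to 0.128 by simulation. The shift is therefore about 0.03/0.128 = 0.2 to 0.105/0.128 = 0.8 standard errors.

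Adding phase as a main effect does not help: in simulation at δ = 0.3, r = 0.5 the shift stayed at 0.076. Adding phase by group removes it but raises the standard error to about 0.1255/√(1−r²). Root-mean-square error without the terms is √(shift² + 0.1255²):

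| δ | r | Shift | Without phase terms | With phase and phase-by-group |
|---|---|---|---|---|
| 0.2 | 0.3 | 0.030 | 0.129 | 0.132 |
| 0.2 | 0.5 | 0.050 | 0.135 | 0.145 |
| 0.2 | 0.7 | 0.070 | 0.144 | 0.176 |
| 0.3 | 0.3 | 0.045 | 0.133 | 0.132 |
| 0.3 | 0.5 | 0.075 | 0.146 | 0.145 |
| 0.3 | 0.7 | 0.105 | 0.164 | 0.176 |

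Simulation with 254 women and 6,000 runs agrees to within about 0.003; at δ = 0.3 it gives 0.149 against 0.148 (r = 0.5) and 0.165 against 0.177 (r = 0.7).

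**Restricting to women not yet on an AI.** If a fraction f qualifies, the standard error rises by 1/√f: 1.15, 1.41 and 2.0 for f = 0.75, 0.50 and 0.25 (assumed).

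**The case for a change.** The best case for a change is that the Time 1 definition is not truncated and still omits the endocrine anchor, so the missing exclusion items do not explain everything. Without the phase terms, the false-positive rate for the E2 interaction would be about 6% to 14% under the assumptions above, and the phase-by-group term restores it. Recording endocrine status at baseline costs little. E2 measured on study is open to post-randomization influence whatever the entry rules say.

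A dilution argument can be added. On assumed inputs (two-sided 5%, SD 1), 127 per arm detects 0.352 SD with 80% power. Power falls to 71%, 61% or 50% if the average effect is 90%, 80% or 70% of that because some women lie outside the AI population.

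Some of this stands. The two descriptions of baseline are not cross-referenced, the E2 time point is open, and bias removal is a real benefit of the extra terms. The rest does not carry:
- The false-positive figures need mixed phases, an exercise effect that differs by phase, and E2 correlated with phase. The documents support none of these, and the shift is zero if either of the first two fails.
- The dilution figures need a share of such women and a smaller effect in them, and neither is documented. Aim 1 in any case targets early stage postmenopausal women generally.
- The post-randomization status of E2 is a separate matter that would arise even if every woman were pre-endocrine at TP1. Nothing in the documents shows that exercise alters E2, and the analysis is already called exploratory.
- Endocrine status may already be collected, given the unseen measures list and the questions asked before the blood draw.

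**Conclusion.** No change is needed. The plan states once that baseline precedes endocrine therapy and does not repeat this in the entry rules that can be read. That is incomplete cross-referencing, with no contradiction shown and no woman shown to be affected. Aim 1 stands: its randomized comparison is unbiased, and the precision loss is at most 3.1% over the range assumed.

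For Aim 3, the possible shift is under one standard error and rests entirely on assumed values of p, δ and r. Compulsory phase interactions would give roughly the same or larger total error, and a subset restriction could double the standard error. Either is a debatable trade for an exploratory question.

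An analyst would in the ordinary course state which E2 measurement was used, show results by TP1 E2 alongside any on-study version, and describe endocrine status at baseline. If the sponsor found that status at TP1 was in fact mixed, a sensitivity analysis with status and its interaction with group would suffice. The covariate provisions in the Preliminary Analyses and the Analysis Plan for Aim 1 leave room for it.
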